7.3.6. Electrocardiograms

A triplicate ECG (3 serial ECGs conducted within approximately 5 to 10 minutes total time) will be performed at Screening to determine eligibility and predose on Cycle 1 Day 1 to serve as baseline. A single ECG will be performed at all remaining time points specified in the SoA (Table 3). A detailed description of the timing of ECGs is provided in Table 10.

Prior to performing the 12-lead ECG, patients will rest in the supine position for at least 5 minutes. When an ECG is to be performed at the same time point as a blood collection, the ECG is to be performed first. The ECG measurement at any time point will be used for AE grading and recommended dose modifications.

Interpretation of the tracing will be made by a qualified physician and documented in the eCRF. QT interval values will be corrected using the QTcF formula. Clinically significant abnormalities present when the patient signed the screening informed consent/assent will be reported in the eCRF. New or worsened clinically significant findings occurring after the screening informed consent/assent must be recorded in the eCRF.

An abnormal ECG (e.g., ECG of > 500 ms or with a change in QTcF from baseline of ≥ 60 ms) may be repeated if it cannot be interpreted by the Investigator. ECG tracings will be

made available if requested by the Sponsor for central assessment by an independent reviewer.

Table 10. Timing of ECGs

Visit	Any Time	Before Morning Dose of Study Treatment	2 Hours (\pm 15 min) After Morning Dose of Study Treatment
Triplicate ECGs			
Screening	X		
Cycle 1 Day 1		X	
Single ECGs			
Cycle 1 Day 1			X
Cycle 2 Day 1		X	X
Subsequent Cycles Day 1		X	X
EOT	X		

7.3.7. Clinical Safety Laboratory Assessments

Blood and urine samples for the laboratory tests listed in [Table 11](#) will be collected at the time points specified in the SoA ([Table 3](#)).

A certified laboratory local to the investigative site will be used for all clinical laboratory assessments for safety (i.e., blood chemistries, hematology, coagulation, serology, renal function, urinalysis), in accordance with the SoA ([Table 3](#)). The investigative site will enter the laboratory results into the eCRF. PK CCI assessments will be sent to a central laboratory in accordance with the SoA and the Laboratory Manual. Information regarding collection, processing and shipping of laboratory assessments is provided in the Laboratory Manual.

The Investigator must review the laboratory report and document this review. The laboratory reports must be filed with the source documents. Additional testing may be required by the Sponsor based on emerging safety data. Additional tests may also be performed if clinically indicated.

Screening laboratory assessments must be performed within 28 days of Cycle 1 Day 1. If performed more than 28 days before Cycle 1 Day 1, then the tests must be repeated, and eligibility confirmed, before study treatment administration on Cycle 1 Day 1. Laboratory assessments collected on Cycle 1 Day 1 must be performed before study treatment administration. After Cycle 1, predose laboratory procedures can be conducted up to 72 hours before study treatment administration (within a 3-day study window), and results will be reviewed by the Investigator or qualified designee and found to be acceptable before study treatment is administered.

Clinically significant abnormal laboratory findings are those which are not associated with the underlying disease, unless judged by the Investigator to be more severe than expected for the patient's condition. All laboratory tests with values considered significantly abnormal during participation in the study or within 30 days after the last dose of study intervention

should be repeated until the values return to normal or baseline or are no longer considered clinically significant by the Investigator.

Electrolyte abnormalities including magnesium should be corrected and cardiac risk factors for QT prolongation (e.g., congestive heart failure, bradyarrhythmias) should be controlled.

Table 11. Summary of Clinical Laboratory Tests

Hematology	Chemistry	Urinalysis	Coagulation	Others
Hemoglobin	Albumin	Appearance	PT	At Screening only:
Hematocrit	Alkaline phosphatase	Color	INR	Hepatitis B surface antigen
RBC	ALT	Specific gravity	PTT or aPTT	Hepatitis B surface antigen antibody
Platelets	Amylase	pH		Hepatitis B core antibody
WBC	AST	Protein		Hepatitis C antibody
Neutrophils	Bicarbonate (CO ₂)	Albumin		HIV, as applicable per local regulations
Lymphocytes	Total bilirubin	Creatinine		
Monocytes	BUN or urea	Glucose		
Eosinophils	Calcium	Ketones		
Basophils	Chloride	Blood		
	CK (If total CK $\geq 3 \times$ ULN, then measure isoenzymes, serum creatinine and myoglobin in blood or urine weekly)	Nitrite		If applicable: Females of childbearing potential require LH, FSH and/or estradiol, serum and urine pregnancy tests as described in the SoA (Table 3).
	Creatinine	Leukocytes		Pregnancy tests (serum or urine) should be repeated if required by local regulations or as clinically indicated.
	Glucose			
	LDH			
	Lipase			
	Phosphate			
	Magnesium			
	Potassium			
	Total protein			
	Sodium			
	Troponin			
	Uric acid			
	Direct bilirubin (if total bilirubin values are abnormal)			

7.3.8. Pregnancy Testing

A serum pregnancy test will be required for all women of childbearing potential (see [Appendix 1](#)) as outlined in the SoA ([Table 3](#)). Urine pregnancy tests will be performed locally as outlined in the SoA, as medically indicated (e.g., in case of loss of menstrual cycle, when pregnancy is suspected), or per country-specific requirement (note that country-required urine pregnancy testing will be outlined and communicated to investigational sites

under separate cover). All blood and urine collections for pregnancy tests occurring on dosing days must be performed prior to study drug administration, with a negative test result required prior to administration of study treatment.

If a urine pregnancy test is positive, the results will be confirmed with a serum pregnancy test. If the serum pregnancy test is negative after a urine test was positive, the Investigator will assess the potential benefit/risk to the patient and determine whether it is in the patient's best interest to resume study treatment and continue participation in the study. Any female patient who becomes pregnant while participating in the study will be instructed to immediately discontinue study treatment. If pregnancy is confirmed by a serum pregnancy test, see [Section 7.4.5.1](#) for reporting requirements.

Patients of nonchildbearing potential (see [Appendix 1](#)) do not require pregnancy tests.

7.3.9. Renal Function Monitoring

Renal function monitoring will be conducted to assess for renal dysfunction at the time points specified in SoA ([Table 3](#)).

See [Section 6.7.3](#) for renal-function-related criteria for modifying or pausing dosing.

7.3.10. Serology

Hepatitis screening assessments will be performed at a local laboratory at the Screening visit to rule out hepatitis infection; required analytes are shown in [Table 11](#). Generally, hepatitis tests will be performed early in the screening process due to the length of time needed to obtain the results. Additional tests may be performed if clinically indicated.

7.3.11. Echocardiogram/Multi-gated Acquisition

Cardiac ejection fraction will be assessed by transthoracic ECHO or MUGA at the time points specified in SoA ([Table 3](#)).

The same method should be used throughout the study. Patients who develop signs/symptoms of congestive heart failure at any point during the study are required to have an evaluation of LVEF measurements by ECHO or MUGA.

7.3.12. Ophthalmic Examination

7.3.12.1. Testing at Screening and During the Treatment Period

Full ophthalmic examination will be performed by an ophthalmologist at Screening ([Table 3](#)), including best corrected visual acuity, slit lamp examination, intraocular pressure, dilated funduscopy and OCT. Examination of the retina is required (especially to identify findings associated with RPED, serous detachment of the retina and RVO). Ophthalmic evaluation may be performed again during the treatment period as clinically indicated.

7.3.12.2. Additional Testing

Patients with clinical suspicion of retinal abnormalities of any grade (e.g., RPED, serous detachment of the retina, RVO, photopsia, metamorphopsia, impairment of visual acuity) must complete at least one of the following additional assessments:

- For non-vascular abnormalities: OCT (spectral domain OCT recommended)
- For vascular abnormalities: fluorescein angiography of the central 30 degrees

Images/results of the ophthalmic examinations (at a minimum, OCT and/or fluorescein angiography) must be sent to the investigational site and be maintained in the patient's source document file. These images/results must be made available upon Sponsor request.

7.4. Adverse Events and Serious Adverse Events

The definitions of an AE and an SAE can be found in [Appendix 7](#).

AEs will be reported by the patient (or, when appropriate, by a caregiver, surrogate, or the patient's legally authorized representative).

The investigator and any qualified designees are responsible for detecting, documenting, and recording events that meet the definition of an AE or SAE and remain responsible to pursue and obtain adequate information both to determine the outcome and to assess whether the event meets the criteria for classification as an SAE or caused the patient to discontinue the study treatment.

The patient will be questioned about the occurrence of AEs in a nonleading manner.

In addition, the investigator may be requested by Pfizer Safety to obtain specific follow up information in an expedited fashion.

7.4.1. Time Period and Frequency for Collecting AE and SAE Information

The time period for actively eliciting and collecting AEs and SAEs ("active collection period") for each patient begins from the time the patient provides informed consent, which is obtained before the patient's participation in the study (ie, before undergoing any study-related procedure and/or receiving study treatment), through and including a minimum of 30 calendar days, except as indicated below, after the last administration of the study treatment.

During the long-term follow-up period in this study for survival, only SAEs will be actively elicited and collected after completion of the active collection period described above. The SAEs identified during long-term follow-up will be reported to Pfizer Safety on the CT SAE Report Form only if considered reasonably related to the study treatment.

Follow-up by the investigator continues throughout and after the active collection period and until the AE or SAE or its sequelae resolve or stabilize at a level acceptable to the investigator and Pfizer concurs with that assessment.

For patients who are screen failures, the active collection period ends when screen failure status is determined.

If the patient withdraws from the study and also withdraws consent for the collection of future information, the active collection period ends when consent is withdrawn.

If a patient definitively discontinues or temporarily discontinues study treatment because of an AE or SAE, the AE or SAE must be recorded on the CRF and the SAE reported using the CT SAE Report Form.

Investigators are not obligated to actively seek AEs or SAEs after the patient has concluded study participation. However, if the investigator learns of any SAE, including a death, at any time after a patient has completed the study, and he/she considers the event to be reasonably related to the study treatment, the investigator must promptly report the SAE to Pfizer using the CT SAE Report Form.

7.4.1.1. Reporting SAEs to Pfizer Safety

All SAEs occurring in a patient during the active collection period as described in [Section 7.4.1](#) are reported to Pfizer Safety on the CT SAE Report Form immediately upon awareness and under no circumstance should this exceed 24 hours, as indicated in [Appendix 7.4](#). The investigator will submit any updated SAE data to the sponsor within 24 hours of it being available.

If a patient begins a new anticancer therapy, SAEs occurring during the above-indicated active collection period must still be reported to Pfizer Safety irrespective of any intervening treatment. Note that a switch to a commercially available version of the study treatment is considered as a new anticancer therapy for the purposes of SAE reporting.

7.4.1.2. Recording Nonserious AEs and SAEs on the CRF

All nonserious AEs and SAEs occurring in a patient during the active collection period, which begins after obtaining informed consent as described in [Section 9.4](#), will be recorded on the AE section of the CRF.

The investigator is to record on the CRF all directly observed and all spontaneously reported AEs and SAEs reported by the patient.

If a patient begins a new anticancer therapy, the recording period for nonserious AEs ends at the time the new treatment is started; however, SAEs must continue to be recorded on the CRF during the above-indicated active collection period. Note that a switch to a commercially available version of the study treatment is considered as a new anticancer therapy for the purposes of SAE reporting.

7.4.2. Methods of Detecting AEs and SAEs

The method of recording, evaluating, and assessing causality of AEs and SAEs and the procedures for completing and transmitting SAE reports are provided in [Appendix 7](#).

Care will be taken not to introduce bias when detecting AEs and/or SAEs. Open ended and nonleading verbal questioning of the patient is the preferred method to inquire about AE occurrences.

7.4.3. Follow-up of AEs and SAEs

After the initial AE/SAE report, the investigator is required to proactively follow each patient at subsequent visits/contacts. For each event, the investigator must pursue and obtain adequate information until resolution, stabilization, the event is otherwise explained, or the patient is lost to follow-up.

In general, follow-up information will include a description of the event in sufficient detail to allow for a complete medical assessment of the case and independent determination of possible causality. Any information relevant to the event, such as concomitant medications and illnesses, must be provided. In the case of a patient death, a summary of available autopsy findings must be submitted as soon as possible to Pfizer Safety.

Further information on follow-up procedures is given in [Appendix 7.3](#).

7.4.4. Regulatory Reporting Requirements for SAEs

Prompt notification by the investigator to the sponsor of an SAE is essential so that legal obligations and ethical responsibilities towards the safety of patients and the safety of a study treatment under clinical investigation are met.

The sponsor has a legal responsibility to notify both the local regulatory authority and other regulatory agencies about the safety of a study treatment under clinical investigation. The sponsor will comply with country-specific regulatory requirements relating to safety reporting to the regulatory authority, IRBs/ECs, and investigators.

Investigator safety reports must be prepared for SUSARs according to local regulatory requirements and sponsor policy and forwarded to investigators as necessary.

An investigator who receives SUSARs or other specific safety information (e.g., summary or listing of SAEs) from the sponsor will review and then file it along with the Investigator Brochure for the study and will notify the IRB/EC, if appropriate according to local requirements.

7.4.5. Exposure During Pregnancy or Breastfeeding and Occupational Exposure

Exposure to the study treatment under study during pregnancy or breastfeeding and occupational exposure are reportable to Pfizer Safety within 24 hours of investigator awareness.

7.4.5.1. Exposure During Pregnancy

An EDP occurs if:

- A female patient is found to be pregnant while receiving or after discontinuing study treatment.
- A male patient who is receiving or has discontinued study treatment exposes a female partner prior to or around the time of conception.
- A female is found to be pregnant while being exposed or having been exposed to study treatment due to environmental exposure. Below are examples of environmental exposure during pregnancy:
 - A female family member or healthcare provider reports that she is pregnant after having been exposed to the study treatment by ingestion.
 - A male family member or healthcare provider who has been exposed to the study treatment by ingestion then exposes his female partner prior to or around the time of conception.

The investigator must report EDP to Pfizer Safety within 24 hours of the investigator's awareness, irrespective of whether an SAE has occurred. The initial information submitted should include the anticipated date of delivery (see below for information related to termination of pregnancy).

- If EDP occurs in a patient or a patient's partner, the investigator must report this information to Pfizer Safety on the CT SAE Report Form and an EDP Supplemental Form, regardless of whether an SAE has occurred. Details of the pregnancy will be collected after the start of study treatment and until 30 days after last dose.
- If EDP occurs in the setting of environmental exposure, the investigator must report information to Pfizer Safety using the CT SAE Report Form and EDP Supplemental Form. Since the exposure information does not pertain to the patient enrolled in the study, the information is not recorded on a CRF; however, a copy of the completed CT SAE Report Form is maintained in the investigator site file.

Follow-up is conducted to obtain general information on the pregnancy and its outcome for all EDP reports with an unknown outcome. The investigator will follow the pregnancy until completion (or until pregnancy termination) and notify Pfizer Safety of the outcome as a

follow-up to the initial EDP Supplemental Form. In the case of a live birth, the structural integrity of the neonate can be assessed at the time of birth. In the event of a termination, the reason(s) for termination should be specified and, if clinically possible, the structural integrity of the terminated fetus should be assessed by gross visual inspection (unless preprocedure test findings are conclusive for a congenital anomaly and the findings are reported).

Abnormal pregnancy outcomes are considered SAEs. If the outcome of the pregnancy meets the criteria for an SAE (ie, ectopic pregnancy, spontaneous abortion, intrauterine fetal demise, neonatal death, or congenital anomaly [in a live-born baby, a terminated fetus, an intrauterine fetal demise, or a neonatal death]), the investigator should follow the procedures for reporting SAEs. Additional information about pregnancy outcomes that are reported to Pfizer Safety as SAEs follows:

- Spontaneous abortion including miscarriage and missed abortion;
- Neonatal deaths that occur within 1 month of birth should be reported, without regard to causality, as SAEs. In addition, infant deaths after 1 month should be reported as SAEs when the investigator assesses the infant death as related or possibly related to exposure to the study treatment.

Additional information regarding the EDP may be requested by the sponsor. Further follow-up of birth outcomes will be handled on a case-by-case basis (e.g., follow-up on preterm infants to identify developmental delays). In the case of paternal exposure, the investigator will provide the patient with the Pregnant Partner Release of Information Form to deliver to his partner. The investigator must document in the source documents that the patient was given the Pregnant Partner Release of Information Form to provide to his partner.

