 - d. **All patients (Safety Lead-In and Phase 2):** If receiving concomitant corticosteroids must be on a stable or decreasing dose (up to a total daily dose of 4 mg of dexamethasone or equivalent) for at least 2 weeks prior to first dose of study treatment.
8. An ECOG PS of 0 or 1 and Karnofsky score ≥ 80 (see [Section 7.2.5](#)).
9. Adequate bone marrow, organ function and laboratory parameters:
 - a. ANC $\geq 1.5 \times 10^9/L$;
 - b. Hemoglobin ≥ 9 g/dL with or without transfusions;
 - c. Platelets $\geq 100 \times 10^9/L$;
 - d. AST and ALT $\leq 2.5 \times ULN$; in patients with liver metastases $\leq 5 \times ULN$;
 - e. Total bilirubin $\leq 1.5 \times ULN$;
Note: Patients with documented Gilbert syndrome or hyperbilirubinemia due to non-hepatic cause (e.g., hemolysis, hematoma) may be enrolled following discussion and agreement with the Sponsor Medical Monitor.

- f. Serum creatinine $\leq 1.5 \times \text{ULN}$; OR calculated creatinine clearance $> 50 \text{ mL/min}$ by Cockcroft-Gault formula; OR estimated glomerular filtration rate $> 50 \text{ mL/min/1.73m}^2$.
10. Female patients of childbearing potential, as described in [Appendix 1](#), must have a negative serum β -HCG test result.
11. Female patients of childbearing potential must agree to protocol-approved methods of contraception, as described in [Appendix 1](#), and to not donate ova from Screening until 30 days after the last dose of study drug.
12. Male patients must agree to use methods of contraception that are highly effective or acceptable, as described in [Appendix 1](#), and to not donate sperm from Screening until 90 days after the last dose of study drug.
13. The patient is deemed by the Investigator to have the initiative and means to comply with scheduled visits, treatment plan and study procedures.

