Appendix 1. Contraceptive Guidance

Female patients of childbearing potential must agree to take appropriate precautions to avoid pregnancy from Screening through 30 days after the last dose of study treatment.

Male patients should use a condom during treatment and through 90 days after the end of systemic exposure to study treatment. If the male patient has a partner that is of child-bearing potential, the partner should also use contraception through 90 days after the end of systemic exposure to study treatment. In addition, male patients must refrain from donating sperm during the study through 90 days after the end of systemic exposure of study treatment. Males who have had a vasectomy qualify as having met the requirement for a highly effective birth control method.

Definitions:

Woman of Childbearing Potential (WOCBP)

A woman is considered fertile following menarche and until becoming post-menopausal unless permanently sterile (see below). If fertility is unclear (e.g., amenorrhea in adolescents or athletes) and a menstrual cycle cannot be confirmed before first dose of study treatment, additional evaluation should be considered.

Women in the following categories are **not** considered WOCBP

1. Premenarchal.
2. Premenopausal female with 1 of the following:
 - Documented hysterectomy.
 - Documented bilateral salpingectomy.
 - Documented bilateral oophorectomy.

For individuals with permanent infertility due to an alternate medical cause other than the above, (e.g., mullerian agenesis androgen insensitivity), Investigator discretion should be applied to determining study entry.

Note: Documentation can come from the site personnel's: review of the patient's medical records, medical examination or medical history interview.

3. Postmenopausal female
 - A postmenopausal state is defined as no menses for 12 months without an alternative medical cause.

- a. A high follicle stimulating hormone (FSH) level in the postmenopausal range may be used to confirm a postmenopausal state in women not using hormonal contraception or hormonal replacement therapy (HRT). However, if patients have less than 12 months of amenorrhea, confirmation of menopause requires more than one FSH measurement.

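### The 30-day limit on collecting pregnancy details is shorter than the 90-day contraception period for male patients and their partners, and conflicts with the rest of Protocol 7.4.5.1

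*Protocol*

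**What the plan says.** **Collection period.** Protocol 7.4.5.1, in the bullet on exposure during pregnancy (EDP) in a patient or a partner, states: "Details of the pregnancy will be collected after the start of study treatment and until 30 days after last dose". One limit serves both sexes.

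**Precaution periods.**
- Female patients (Appendix 1): "precautions to avoid pregnancy from Screening through 30 days after the last dose of study treatment".
- Male patients (Appendix 1): "Male patients should use a condom during treatment and through 90 days after the end of systemic exposure to study treatment".
- Partners of child-bearing potential (Appendix 1): "the partner should also use contraception through 90 days after the end of systemic exposure to study treatment".
- Sperm donation (inclusion criterion 12): "to not donate sperm from Screening until 90 days after the last dose of study drug". Appendix 1 repeats this restriction but counts the 90 days from the end of systemic exposure.

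**Other duties in 7.4.5.1.** The definition of EDP includes this case: "A male patient who is receiving or has discontinued study treatment exposes a female partner prior to or around the time of conception". It has no day limit. On reporting: "The investigator must report EDP to Pfizer Safety within 24 hours of the investigator's awareness, irrespective of whether an SAE has occurred". The section then has the investigator follow the pregnancy until it completes or is terminated, and adds a release form for the partner where exposure was paternal.

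**What is asked after treatment.** Section 7.2.4.3 lists three items for survival contacts, at least every 12 weeks: new related SAEs, later anticancer therapies and survival status. Section 7.4.1 says that after the active collection period, which runs for at least 30 days after last dose, only SAEs are actively elicited.

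**The concern.** The 30-day limit appears to have been set with female patients in mind and then applied to partners as well. A partner pregnancy arising between Day 31 and Day 90 falls in a period when the protocol still asks the couple to use contraception, but after the stated end of collection. A site that takes the sentence at face value has an apparent reason not to ask, or not to complete the form.

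Section 2.2.3 lists embryo-fetal toxicity as an important potential effect of the combination. Few pregnancies are to be expected, so each one that goes unrecorded matters to the safety record. Nothing statistical depends on the point. No endpoint, analysis set or sample size uses these data, and SAP 6.6.10 only lists pregnancy test results.

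**Working it through.** The plan gives no figure of its own to reproduce. The check compares date windows and then sets the provisions side by side.

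**Inputs**
- Stated end of collection: 30 days after last dose (7.4.5.1).
- Female precaution period: 30 days after last dose (Appendix 1).
- Male and partner period: 90 days, from last dose (inclusion criterion 12, sperm donation) or from end of systemic exposure (Appendix 1).
- Lag from last dose to end of systemic exposure: not given; assumed 0 to 7 days.

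**Days outside the stated collection period**
- Female patients: 30 − 30 = 0 days.
- Male patients and partners, from last dose: 90 − 30 = 60 days, and 60/90 = 66.7% of the post-treatment period.
- Male patients and partners, from end of systemic exposure: with a 0-day lag, 60/90 = 66.7%; with a 7-day lag, (97 − 30)/97 = 67/97 = 69.1%.

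**Share of the whole male precaution period.** Appendix 1 also covers time on treatment, so the 60 days can be set against treatment plus 90 days, for assumed treatment durations:

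| Treatment (days, assumed) | 60/(treatment + 90) |
|---|---|
| 28 | 60/118 = 51% |
| 84 | 60/174 = 34% |
| 168 | 60/258 = 23% |
| 336 | 60/426 = 14% |

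**What the 30-day sentence could mean**
1. *It limits which pregnancies are in scope.* Partner pregnancies on Days 31 to 90 are then excluded, although the EDP definition in the same section includes men who have stopped treatment.
2. *It limits how long details are gathered.* It then contradicts follow-up to completion, and it does so for female patients too, because 30 days after last dose would come before most pregnancies end.
3. *It limits routine active collection only,* in parallel with the 30-day minimum in 7.4.1. It is then compatible with the open-ended reporting duty, but active collection still stops before the 90-day period does.

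The first two readings contradict other text in 7.4.5.1. The third does not, but the protocol does not state it, and it leaves the mismatch for male patients and partners in place.

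**Whether other procedures close the gap.** The reporting duty depends on the investigator's awareness. A partner pregnancy is not in itself an SAE; 7.4.5.1 treats abnormal outcomes as SAEs. The SAE-only questioning in 7.2.4.3 and 7.4.1 would therefore not be expected to bring out an uncomplicated partner pregnancy.

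**The case against.** A reader might infer that partner pregnancies after Day 30 are not followed at all, or that two thirds of the relevant data are lost. The documents do not support either inference. A partner pregnancy on Day 60 that reaches the investigator meets the EDP definition, must be reported within 24 hours, and is followed to its end. Sections 7.4.5 and 7.4.5.1 put no end date on that duty, and the reporting table in Appendix 7.3 marks all such exposures as reportable. There are further backstops: abnormal outcomes are SAEs, SAEs are still elicited during survival follow-up with related ones reported, and related SAEs learned of after study completion must also be reported.

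The 66.7% is a ratio of calendar days. Reading it as a loss would assume no reporting after Day 30, which these provisions contradict. It also leaves out time on treatment; with that included, the share is 14% to 51% under the durations assumed above.

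It is also fair to say that the 30-day sentence can hardly have been meant as a hard stop, since that would cut off most pregnancies in female patients before delivery. All of this stands, and it limits the point to conflicting wording and a lack of active questioning. It does not remove the point. The backstops rely on awareness or on an abnormal outcome, and a site still has to choose between a sentence that ends collection at 30 days and others that do not.

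**Conclusion.** The inconsistency is real and minor. The single 30-day limit matches the female precaution period but ends 60 days before the male and partner period does, counted from last dose (60 to 67 days if counted from end of systemic exposure, with an assumed lag of 0 to 7 days). It also conflicts with the paternal EDP definition, the reporting duty and follow-up to completion in the same section. The 90 days themselves have two different start points in the protocol. In practice, sites receive conflicting instructions, and no listed procedure asks about partner pregnancy after Day 30. Known exposures remain reportable at any time.

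The conclusion rests on the text alone. The lag and treatment durations are assumptions used only to show a range. No view is taken on which contraception duration is right; the 30 and 90 days are the protocol's own.

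**What to change.** Reconcile inclusion criterion 12, section 7.4.5.1 and Appendix 1 so that:
- the period for collecting pregnancies is no shorter than the contraception period the protocol states for each sex;
- the male and partner period has one start point, either last dose or end of systemic exposure, used throughout;
- 7.4.5.1 separates which pregnancies are collected from how long each is followed, and says that details of any reported pregnancy are collected to outcome.

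If the longer male and partner period is to be actively covered, the survival contacts already scheduled at least every 12 weeks could carry the question.

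The cost is a sentence or two in the protocol and matching instructions for the EDP form. Nothing in the SAP, sample size or primary analysis changes.
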